5.5 Analysis Plan for Exploratory Objectives

- Excel Table 7 describes the change in 4 patient satisfaction questions at weeks 12 and 24 after the initiation of adalimumab, in those patients continuing on adalimumab (observed population). These changes will be summarized as number and percentage of each response and compared with Wilcoxon signed rank test shown by p-value1. Satisfaction will also be dichotomized and analyzed over time with Cochran-Armitage test for trends shown by p-value2 in the table.
- Excel Table 8 summarizes the patients' global impression of change in RA at weeks 12 and 24 after the initiation of adalimumab, in those patients continuing on adalimumab (as observed population). Each response (very much better, much better, a little better, no change, a little worse, much worse, and very much worse) will be summarized as number and percentage.
- Descriptive statistics will be presented for post-index overall RA related direct healthcare resource utilization (Excel Table 9)
 - Consultations/visits to healthcare professionals for treatment of RA (number of patients with ≥ 1 visit; categorized by the treatment department listed in 3.5.4)
 - Procedures received when visiting the healthcare professional(s) for treatment of RA (number of patients with ≥ 1 procedure; categories listed in 3.5.4)
 - surgeries received when visiting the healthcare professional(s) for treatment of RA (number of patients with ≥ 1 surgery; categories listed in 3.5.4)
 - Hospitalizations in relation to RA (number of patients with ≥ 1 admission)
 - Length of stay in days (mean, SD, median)
 - Concomitant medications taken for RA (number of patients with ≥ 1 medication; categories listed in 3.5.4))
- Associations between disease severity (measured by DAS28) and PROs (HAQ DI score, SF-36 domain scales, EQ-5D-3L index, WPAI outcomes) will be analyzed using the bivariate linear regression model (Excel Table 10.1). Separate models will be estimated to identify the association between DAS28 and each of the PROs.
- Additionally, in Excel Table 10.2, separate bivariate liner regression models will be estimated to identify the association between change in DAS28 and change in each of the PROs at 12 and 24 weeks after baseline respectively.

- In Excel Table 11, separate multivariate generalized linear models (GLM) will be estimated to test for the differential changes in primary and secondary efficacy outcomes after baseline, across the subgroups defined by the potential modifiers, including age, gender, baseline severity, and other diagnoses/comorbidities.

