approximately 70 days after the Week 24 dosing or the last dose of adalimumab to determine the status of any ongoing AEs/SAEs or the occurrence of any new AEs/SAEs. The information will be recorded on the appropriate in eCRF page.

For subjects that are considered lost to follow-up, reasonable attempts must be made to obtain information on the final status of the subject. At a minimum, two phone calls must be made and one certified letter must be sent.

9.3 **Variables**

Variables (as observed):

Primary Variable

- Change in HAQ DI score at week 24 from baseline

Secondary Variable

- Change in other PROs (SF-36 domain scales, EQ-5D Index, Work Productivity and Activity Impairment Questionnaire [WPAI]) from baseline to weeks 12 and 24
- Change in HAQ DI score at week 12 from baseline
- Number and percent of patients achieving a clinically meaningful improvement on the HAQ DI, from baseline to weeks 12 and 24
- Healthcare Resource Utilization (HCRU) at baseline, 12 and 24 weeks

Exploratory Variable

- Difference of the change in HAQ DI score from baseline to 24 weeks between as observed population and withdrawal population
- Change in patient satisfaction questions from baseline to weeks 12 and 24
- Patient's impression of change at weeks 12 and 24 from baseline
- Association between disease severity and PROs
- Association between change in disease severity and change in PROs

9.4 **Data Sources**

Case Report Forms (CRFs) and patient questionnaires.

Collection of data includes but not limited to subject demographics, clinical history, comorbidities, spontaneous adverse events, and concomitant medications. The following questionnaires will be utilized to collect data directly from participating subjects:

- EQ-5D
- SF-36
- HAQ DI
- WPAI

- HCRU
- Patient Global Impression of Change (PGIC)
- Patient Treatment Satisfaction Questions

9.5 **Study Size**

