9.7.3 Planned Methods of Statistical Analysis

All statistical tests will be two-tailed with a significance level of 0.05. Descriptive statistics will be provided. Descriptive analysis will be conducted on all key parameters and presented as mean, standard deviation, minimum, maximum, and median when continuous and as "n" and percent when categorical. Change from adalimumab initiation to 24 weeks will be calculated and evaluated for significant improvements using paired t-tests / ANOVA for parametric and Wilcoxon signed-rank for non-parametric data. Analysis will be also be conducted by severity level (moderate vs severe), disease duration quartile (to compare to prior work) and up to two (2) other subgroups. Cochran-Armitage test of trends or other similar methods may be used to compare categories of subjects.

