2.3 Exploratory Objectives

- To describe the change in HAQ DI score at 24 weeks after the initiation of adalimumab, in those patients continuing on adalimumab (as observed population), compared with those patients not continuing on adalimumab (withdrawal population). The mean changes in these two groups will be compared using an independent t-test.
- Patient's impression of change in RA at weeks 12 and 24 after the initiation of adalimumab, in those patients continuing on adalimumab (as observed population). Each response will be summarized as number and percentage.
- To summarize the healthcare resource utilization using number and percentage within each category (number of consultations, number of procedures received, number of surgeries, number of hospitalizations and length of stay, number and type of concomitant medications)

- To summarize the change in patient satisfaction questions at weeks 12 and 24 after the initiation of adalimumab, in those patients continuing on adalimumab (as observed population). These changes will be summarized as number and percentage of each response and compared with Wilcoxon signed rank test. Satisfaction will also be dichotomized and analyzed over time with Cochrane-Armitage test for trends.
- To analyze the associations between disease severity and PROs (HAQ DI, SF-36 domain scales, EQ-5D-3L index, WPAI total lost productivity)
- To analyze the associations between change in disease severity and change in PROs (HAQ DI, SF-36 domain scales, EQ-5D-3L index, WPAI total lost productivity)
- To explore the potential modifying effects of baseline measures on the changes in primary and secondary efficacy outcomes (i.e. PROs). These measures will include age, gender, baseline severity, and other diagnoses/co-morbidities.

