3. STUDY DESIGN

3.1 Overview of Study Design

This study is designed as a prospective, observational study to assess the effect of adalimumab on health-related QoL and work productivity in patients with RA in Taiwan in clinical practice.

This study is non-interventional. Patient therapy is not decided by the study protocol but falls within current medical practice, and the prescription of adalimumab is clearly separated from the decision to include the patient in this study. The subjects/investigator will follow the current clinical practice in each site and also the routine clinical follow up as determined by the treating physician.

RA patients will be recruited from within the clinical settings of each rheumatologist participating in the study. Approximately 100 patients diagnosed with RA that meet the inclusion and exclusion criteria will be enrolled at up to 7 sites in Taiwan.

To assess health and disability outcomes, the HAQ DI will be assessed at baseline, Week 12 and Week 24 after treatment initiation with adalimumab. In addition, other PROs of work activity and well-being, including the WPAI, EQ-5D-3L, and SF-36, will also be collected. All above instruments have been validated for the Chinese version.

The patients identified by the recruiting investigators based on the study selection criteria will complete a set of patient questionnaires on QoL, functioning, work

productivity, treatment satisfaction, impression of change and HCRU. Data will be captured at baseline (D0), Week 12 and Week 24.

The HCRU will also be collected. This includes surgical procedures, hospitalizations, bed days in hospital, physician consultations etc. Costs will be assigned based on the HCRU using standardized costs for each participating centers.

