4. SAMPLE SIZE AND POWER

Approximately 100 patients diagnosed with RA will be recruited. The sample size was calculated by assuming an alpha of 0.05 and a power of 0.80 in a two-sided test, resulting in 52 subjects required to recognize a statistically significant improvement in HAQ DI (-0.21) (11). Given the importance of other secondary endpoints, an improvement of 9.9 ± 25 hours of work time lost requires 58 subjects, assuming an alpha of 0.05 and a power of 0.80 in a two-sided test (12). However, since it is expected that approximately half the study population may no longer be working due to their age, approximately twice this number (100 patients) will be required to achieve the required number of respondents. We have also assumed a drop-out rate of 13% (assuming between 10%-15%).

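### The Cochran-Armitage test on satisfaction over time treats repeated answers from the same patients as independent, so p-value2 in Table 7 has the wrong variance unless the within-patient correlation is zero

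*SAP*

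**What the plan says.** SAP 5.5 describes Table 7, which reports the four treatment satisfaction questions in a single group ("in those patients continuing on adalimumab (observed population"). Two p-values are planned. The five-level responses are "compared with Wilcoxon signed rank test shown by p-value1". The next sentence adds the second: "Satisfaction will also be dichotomized and analyzed over time with Cochran-Armitage test for trends shown by p-value2 in the table". SAP 2.3 words it almost identically: "Satisfaction will also be dichotomized and analyzed over time with Cochrane-Armitage test for trends". The same sentence appears three times in the protocol: in the abstract (4.0), in Study Design (9.1) and in Exploratory Endpoint Analysis (9.7.6).

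The visits are fixed in SAP 3.1: "Data will be captured at baseline (D0), Week 12 and Week 24". The schedule of events (Protocol 9.1.1) has the satisfaction questions at all three visits, and Protocol 9.3 defines the variable as "Change in patient satisfaction questions from baseline to weeks 12 and 24". Protocol 9.7.3 sets the level: "All statistical tests will be two-tailed with a significance level of 0.05".

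Neither document names a repeated-measures version of the trend test, the cut-point for calling a patient satisfied, the satisfaction rates expected, or the correlation between a patient's answers.

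**The concern.** Cochran-Armitage compares proportions across ordered groups made up of different, independent subjects. Here the groups are three visits of one cohort. Each patient contributes an answer to every group, and the test's variance leaves out the covariance between those answers.

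The SAP accepts this principle for the same items. The protocol had planned Kruskal-Wallis for the five-level responses; the SAP replaced it with the paired Wilcoxon signed rank test but kept the independent-groups test for the dichotomised version. Table 7 would then give two p-values for the same answers, one treating them as paired and one as unpaired. A modest real shift could show a significant p-value1 beside a non-significant p-value2, and part of that disagreement would come from the variance formula rather than from the data.

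**Working it through.** The plan gives no figure for this test, so there is none to reproduce.

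**Inputs from the documents.** Three visits at 0, 12 and 24 weeks; two-sided alpha of 0.05; about 100 patients ("Approximately 100 patients diagnosed with RA will be recruited") with the protocol's 10% dropout, so n = 90.

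**Assumptions.** The correlation rho between a patient's dichotomised answers at baseline and Week 24, and the proportions satisfied.

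**Step 1: what the statistic measures.** With complete data and equally spaced visits, the middle visit has zero weight. The numerator is proportional to the sum over patients of (Week 24 answer minus baseline answer).

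**Step 2: its variance under no change, with common proportion p.**
- Used by Cochran-Armitage: 2np(1 − p)
- True value: 2np(1 − p)(1 − rho)

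The test statistic therefore has variance 1 − rho instead of 1.

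**Step 3: true two-sided size** = 2 × [1 − Φ(1.96/√(1 − rho))].

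| rho (assumed) | 1.96/√(1 − rho) | True size |
|---|---|---|
| 0 | 1.960 | 5.0% |
| 0.1 | 2.066 | 3.9% |
| 0.2 | 2.191 | 2.8% |
| 0.3 | 2.343 | 1.9% |
| 0.5 | 2.772 | 0.6% |
| −0.2 | 1.789 | 7.4% |

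Simulation (20,000 data sets per setting; proportions 0.3, 0.5 and 0.7; n = 90 complete) gives 3.5% to 3.8% at rho 0.1, 1.6% to 1.8% at 0.3 and 0.4% to 0.7% at 0.5. With 100, 95 and 90 patients at the three visits the results are close to these. The same trend score with a patient-clustered variance has size 4.2% to 5.4% in every null setting.

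**Step 4: power for an assumed rise of 40%, 47.5% and 55%, n = 90.** The difference is 0.15.
- Cochran-Armitage standard error: √(2 × 0.475 × 0.525/90) = 0.0744, whatever rho is. Then z = 0.15/0.0744 = 2.02, and power is a little over one half.
- True standard error: √{[0.24 + 0.2475 − 2 rho √(0.24 × 0.2475)]/90} = 0.0698, 0.0616 and 0.0520 at rho 0.1, 0.3 and 0.5.
- Paired-test power, Φ(0.15/SE − 1.96): about 57%, 68% and 82%.

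Simulation of Cochran-Armitage against McNemar on baseline and Week 24 agrees:

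| rho (approx.) | Cochran-Armitage | Paired test |
|---|---|---|
| 0.1 | 51% | 56% |
| 0.3 | 51% | 69% |
| 0.5 | 51% | 81% |

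**Step 5: a large rise, 40%, 55% and 70%.** Both tests have power of about 99% or more at rho 0.1 to 0.5, so the loss is negligible.

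**The case against.** The strongest reply concerns size and consequence, since the mismatch between test and data is plain from the text.

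- **Strength.** A reader might infer that the test is strongly conservative. The documents do not support that, because they give no correlation. A low one is plausible: adalimumab starts at the baseline visit and the questions look back four weeks, so the baseline answer rates the earlier treatment and the Week 24 answer rates treatment that includes adalimumab. At rho 0.1 the size is 3.9%, a mild loss. This stands.
- **Every p-value2 wrong.** This is also too strong. The size is correct at zero correlation, and a negative correlation would make the test anti-conservative.
- **Consequence.** The analysis is listed as exploratory, the questions are described as not validated, positive correlation cannot inflate false positives, and the Wilcoxon p-value beside it is valid. This stands, with one qualification: the introduction to SAP 5.4 also counts satisfaction among the secondary outcome measures, so the p-values may carry more weight than the exploratory label suggests.
- **Scope.** A reader might extend the point to Protocol 9.7.3, which also mentions Cochran-Armitage. That sentence is permissive and concerns comparing categories of subjects, which are independent groups, so the objection does not reach it.

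None of this makes the independence variance right for repeated answers.

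**Conclusion.** The point holds, with limited consequence. As written, p-value2 rests on a variance that is correct only if a patient's answers at different visits are uncorrelated. With positive correlation the test is conservative: true size is about 3.9% to 0.6% for assumed correlations of 0.1 to 0.5. Against a modest assumed rise, the power given up runs from about 5 percentage points (51% against 56%) to about 30 (51% against 81%); against a large rise it is negligible. These figures assume 90 complete patients and equally spaced visits, and the correlations and satisfaction rates are not in the documents. The primary analysis and the powered endpoints are unaffected.

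**What to change.** In SAP 2.3 and 5.5 and in Protocol 4.0 (abstract), 9.1 and 9.7.6, replace Cochran-Armitage for satisfaction over time with a logistic GEE that has visit as a linear term and robust standard errors clustered on patient. This keeps the trend question and uses the right variance. McNemar tests against baseline would also be valid, but they do not test a trend and largely repeat the paired comparisons behind p-value1.

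State the cut-point in the same edit, in particular whether the neutral middle response counts as satisfied. Without it p-value2 cannot be reproduced under any test. Leave Protocol 9.7.3 unchanged.

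The cost is one sentence in each of five places, a cut-point definition and a different SAS procedure. No new data are needed.

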4.0 Abstract

Title: Real-World Outcome of Adalimumab on Rheumatoid Arthritis Patients in Taiwan.

Rationale and Background: Given the requirement to keep a balance between effectiveness and cost containment to ensure that the available health resources are used in a cost-effective manner, there is an increasing demand for real-world evidence (RWE) from policy makers, regulators, providers and payers in the region to optimize spending and patient outcomes.

So far, there are no data available regarding adalimumab's impact on patients' quality of life (QoL) and healthcare resource utilization (HCRU) in a realistic study design, which provides greater generalization in Taiwan.

The goal of this study is to determine the QoL, HCRU and costs of the patients care in subjects with RA who are treated with adalimumab in these three countries.

Results from study on the impact of adalimumab on Work Productivity and Activity Impairment (WPAI) scores and other Patient-Reported Outcomes (PROs) will be of interest to a variety of stakeholders in the healthcare system including patients, healthcare practitioners and payers in Taiwan.

Research Question and Objectives: The objective of this non-interventional, observational study is to assess the impact of adalimumab on health-related QoL and work productivity in patients with Rheumatoid Arthritis (RA) in Taiwan. Specifically, to achieve the above objective the following concrete steps will be taken:

1. Recruit investigators who are willing and able to recruit and follow new adalimumab users for 6 months follow-up
2. Collect the patients' clinical profile, patient-reported QoL, functioning, work productivity, treatment satisfaction and HCRU of RA patients at adalimumab initiation
3. Follow the patients initiating adalimumab for 24 weeks and identify the changes in clinical, economic, and PROs associated with adalimumab

Study Design: The study is designed as a prospective, observational study to assess the effect of adalimumab on health-related QoL and work productivity in patients with RA in Taiwan.

Note: This study is non-interventional and the subjects/investigators will follow the current clinical practice in each site and also the routine clinical follow up as determine by the treating physician.

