 ₁₃ Aspirin (ASA)	_____	_____ mg	_____
 ₁₄ Diclofenac (Voltaren)	_____	_____ mg	_____

1023259 HCRU Questionnaire (Baseline) v8_0

6

1023259 Real-World Impact of RA
[Site number] - [Participant ID]

7. In the last 6 months, have you taken any medications for your rheumatoid arthritis?			
Drug name	Average number of pills per day	Dose strength	Times per month
 ₁₅ Indomethacin (Indocid)	_____	_____ mg	_____
 ₁₆ Others	_____	_____ mg	_____
Others			
 ₁₇ Steroids	_____	_____ mg	_____
 ₁₈ Stomach or gastric medications	_____	_____ mg	_____

1023259 Real-World Impact of RA
[Site number] - [Participant ID]

8. In the last 6 months, were you hospitalized in relation to your rheumatoid arthritis other than surgery? If yes, how many days did you stay at the hospital for your rheumatoid arthritis?		
 No hospitalization in the last 6 months		
Most recent hospitalization Admission date:  / /  (DD/MM/YYYY)	 ₁ Intensive care unit (ICU)  ₂ General ward  ₃ Both  ₄ Other: _____	 Total days in hospital
Next hospitalization Admission date:  / /  (DD/MM/YYYY)	 ₁ Intensive care unit (ICU)  ₂ General ward  ₃ Both  ₄ Other: _____	 Total days in hospital
Next hospitalization Admission date:  / /  (DD/MM/YYYY)	 ₁ Intensive care unit (ICU)  ₂ General ward  ₃ Both  ₄ Other: _____	 Total days in hospital

1023259 Real-World Impact of RA

Site number	-	Participant ID
-------------	---	----------------

9. Please check all the medical conditions you have been diagnosed with.

- ₀ No comorbidity
- ₁ Myocardial infarction
- ₂ Congestive heart failure
- ₃ Peripheral vascular disease
- ₄ Cerebrovascular disease
- ₅ Dementia
- ₆ Chronic pulmonary disease
- ₇ Connective tissue disease
- ₈ Ulcer disease
- ₉ Mild liver disease
- ₁₀ Diabetes
- ₁₁ Hemiplegia
- ₁₂ Moderate or severe renal disease
- ₁₃ Diabetes with end-organ damage
- ₁₄ Any tumor
- ₁₅ Leukemia
- ₁₆ Lymphoma
- ₁₇ Moderate or severe liver disease
- ₁₈ Metastatic solid tumor
- ₁₉ AIDS

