 ₁ Auranofin (Ridaura, Myochrysine)	_____	_____ mg	_____
 ₂ Azathioprine (Imuran)	_____	_____ mg	_____
 ₃ Cyclosporine (Sandimmune and Neoral)	_____	_____ mg	_____
 ₄ Hydroxychloroquine (Plaquenil)	_____	_____ mg	_____
 ₅ Leflunomide (Arava)	_____	_____ mg	_____
 ₆ Methotrexate (Rheumatrex, Folex)	_____	_____ mg	_____
 ₇ Minocycline (Minocin, Dynacin and Vectrin)	_____	_____ mg	_____
 ₈ Sulfasalazine (Azulfidine)	_____	_____ mg	_____
 ₉ Others	_____	_____ mg	_____
Anti-inflammatory Drug (NSAID)			
 ₁₀ Ibuprofen (Advil, Motrin, Nuprin)	_____	_____ mg	_____
 ₁₁ Naproxen (Naprosyn, Anaprox, Aleve)	_____	_____ mg	_____
 ₁₂ Celecoxib (Celebrex)	_____	_____ mg	_____
 ₁₃ Aspirin (ASA)	_____	_____ mg	_____
 ₁₄ Diclofenac (Voltaren)	_____	_____ mg	_____

1023259 HCRU Questionnaire (Follow-up) v8_0

6

1023259 Real-World Impact of RA
[REDACTED]
Site number - Participant ID

6. Since you last filled out this questionnaire, have you taken any medications for your rheumatoid arthritis?			
Drug name	Average number of pills per day	Dose strength	Times per month
 ₁₅ Indomethacin (Indocid)	_____	_____ mg	_____
 ₁₆ Others	_____	_____ mg	_____
Others			
 ₁₇ Steroids	_____	_____ mg	_____
 ₁₈ Stomach or gastric medications	_____	_____ mg	_____

1023259 Real-World Impact of RA

Site number	-	Participant ID
-------------	---	----------------

7. Since you last filled out this questionnaire, when you were hospitalized in relation to your rheumatoid arthritis, how many days did you stay at the hospital for your rheumatoid arthritis		
 No hospitalization since you last filled out this questionnaire		
Most recent hospitalization Admission date:   /   /   (DD/MM/YYYY)	 1 Intensive care unit (ICU)  2 General ward  3 Both  4 Other: _____	 Total days in hospital

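### SAP Table 9 reports five of its six resource-use lines only as patients with at least one event, although counts are declared and collected, and the promised costs have no analysis

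*SAP*

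**What the plan says.** SAP 2.3 sets the resource-use objective in terms of "number of consultations, number of procedures received, number of surgeries, number of hospitalizations and length of stay", together with the number and type of concomitant medications, to be shown as number and percentage per category. Protocol 9.7.6 names almost the same list. SAP 3.5.4 derives each item as a number, by department, procedure type, surgery type or drug, plus total hospital days.

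SAP 5.5 then specifies Table 9. Consultations become "number of patients with ≥ 1 visit; categorized by the treatment department listed in 3.5.4", procedures "number of patients with ≥ 1 procedure; categories listed in 3.5.4" and surgeries "number of patients with ≥ 1 surgery; categories listed in 3.5.4". Hospitalizations and medications follow the same pattern. Length of stay alone is given as mean, SD and median. SAP 3.5 sets the period as the six months after the index date.

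On costs, SAP 3.1 states "Costs will be assigned based on the HCRU using standardized costs for each participating centers", and Protocol 4.0 and 9.1 say the same. The protocol abstract also gives as the study's goal to "determine the QoL, HCRU and costs of the patients care in subjects with RA who are treated with adalimumab".

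**The concern.** A yes/no flag for each category discards volume, which is what a resource-use description is for. The patients are seen regularly by the rheumatologists who recruited them, so for that department the flag is settled by the visit schedule and says nothing about intensity of care. Volume is also the input to any cost figure, and the documents promise one. Payers and reimbursement are named in the rationale of both documents as the use of this evidence, so a table that cannot separate light from heavy use would leave that aim largely undescribed.

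**Working it through.** The documents state no resource-use or cost figure, so there is nothing to reproduce. The check compares sections and then illustrates what a flag can and cannot show.

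**1. Declared, collected and planned quantities**

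| Item | Declared (SAP 2.3, 3.5.4) | Follow-up patient form (Protocol Appendix J) | Table 9 (SAP 5.5) |
|---|---|---|---|
| Consultations | number, by department | number of times per department (Q1) | patients with ≥1 |
| Procedures | number | number of times per procedure (Q2) | patients with ≥1 |
| Surgeries | number | up to five entries with type, stay and date (Q3) | patients with ≥1 |
| Hospitalizations | number | up to three admissions (Q7) | patients with ≥1 |
| Medications | number | tick list with dose and frequency (Q6) | patients with ≥1 |
| Length of stay | total days | total days per admission (Q7) | mean, SD, median |

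Five of six lines are flags. The counts exist on the forms and in the derived variables but reach no listed output.

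**2. The rheumatologist row**

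- Patients are recruited in rheumatologists' clinics (Protocol 9.1, SAP 3.1).
- At Weeks 12 and 24 the questionnaires are collected before the physician is seen (Protocol 9.2.4.6, SAP 3.3.2).
- The follow-up form covers the time since the previous form.

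The Week 12 visit comes after the Week 12 form and so falls in the recall period of the Week 24 form. Anyone who attends Week 12 and completes the Week 24 form correctly has at least one rheumatologist visit. If all n such patients are flagged, the row reads 100%, with exact 95% lower limit 0.025^(1/n):

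- n = 87 (100 less the SAP's 13% drop-out): 95.8%
- n = 90 (100 less the protocol's 10%): 96.0%
- n = 100: 96.4%

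With assumed numbers, 2 and 6 visits per patient differ by 6 / 2 = 3 in volume, and both read 100%.

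**3. The other rows**

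Without a scheduled visit behind it, a row need not be near 100%. If contacts were Poisson with mean m, the flagged share would be 1 − exp(−m). All rates here are assumed:

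- m = 0.1: 9.5%
- m = 0.5: 39%
- m = 1: 63%
- m = 2: 86%

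Such a flag is informative but does not determine the count. Take 30% flagged, so the proportion with none is 0.7:

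- Poisson: m = −ln(0.7) = 0.36 contacts per patient.
- Negative binomial with k = 0.2: m = k × (0.7^(−1/k) − 1) = 0.2 × (0.7^(−5) − 1) = 0.99.

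The same table entry fits a range of 0.99 / 0.36 ≈ 2.8-fold in volume.

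**4. Costs**

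Protocol 9.7, SAP 5 and the table list in SAP 6 contain no cost method and no cost table. No unit-cost source or price year is given anywhere.

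**The case against.** The best defence is that Table 9 is descriptive and untested, and that Protocol 9.7.6 and SAP 2.3 treat it as exploratory (although Protocol 9.3 lists resource use among the secondary variables). No inferential result depends on it. For rare events such as surgery or admission, the percentage with at least one is a sensible summary. SAP 5.1 also lets the tables change, and the table-shell workbook is not among the documents, so its rows cannot be checked. This limits the weight of the point, but the mismatch within the SAP stands: the counts it derives are not in the analysis it specifies. Leave to alter tables once results are seen is no substitute for listing them beforehand.

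Four stronger readings are tempting and not supported.

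- A reader might infer that the visit schedule pushes resource use in general to the ceiling. This is shown only for the rheumatologist and any-visit rows, among patients who attend Week 12 and complete the Week 24 form.
- A reader might infer that counts cannot be reported. They are collected and derived; they are only not listed in SAP 5.5.
- A reader might infer that length of stay is corrupted. The baseline item asks "In the last 6 months, were you hospitalized in relation to your rheumatoid arthritis other than surgery", while follow-up Q7 asks "when you were hospitalized in relation to your rheumatoid arthritis, how many days did you stay at the hospital" with no such exclusion. Table 9 is post-index only, so the baseline item never enters it. Nor does any text tell the analyst to add the surgical stay in follow-up Q3 to the days in Q7, so double counting of surgical days is not part of the plan.
- A reader might infer that costs are a main objective left unmet. The abstract's goal sentence goes on to mention three countries in a single-country study, so it may be carried-over text. Costs do not appear in the objectives in Protocol 8.0 or SAP 2, or in the variables in Protocol 9.3. What remains is a repeated promise with no analysis behind it.

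**Conclusion.** The point holds as a mismatch between what is declared and what is planned. Five of the six Table 9 lines omit the counts declared in SAP 2.3 and 3.5.4. One department row of the nine, and any any-visit row, is near 100% by design. That rests on the patient attending Week 12 and reporting the visit correctly at Week 24. Patients who leave early or skip the form can fall outside it, hence close to 100% and not exactly 100%. The threefold and 2.8-fold figures depend on assumed visit numbers and distributions and show only that flags do not fix volume. Planned cost tables: none. The change is worth making because it lets the study describe the volume of care it says it will describe. The primary and other tested endpoints are unaffected.

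**What to change.** 1. In SAP 5.5 and Table 9, add the number of contacts per patient (mean, SD, median, range) for each category in SAP 3.5.4, and keep the percentages with at least one beside them.
2. State that length of stay is taken from the total-days field of follow-up Q7, without adding the surgical stay from Q3.
3. Either specify the cost analysis (unit-cost source, price year, counts multiplied by unit costs, and a table to hold it) or delete the cost statements from Protocol 4.0 and 9.1 and SAP 3.1.

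Items 1 and 2 cost some SAP wording and a few descriptive rows, from data already collected. Item 3 costs more if the statements are kept, because unit costs must be sourced and the analysis designed; deleting them costs only an edit. No form change is proposed. Data collection was planned to end on 31 January 2017 and the SAP cites table shells dated January 2018, so on those dates a revised form would come too late.
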